Research data will be managed in REDCap, (Research Electronic Data Capture), a secure, web-based, HIPAA-compliant data collection platform, which is password protected and accessible only to the research team. Information linking subjects with their unique identifier will be kept in the REDCap database, with access restricted to study personnel. Study data, by necessity, will include personal identifiers, in order to schedule and track study visits and collect medical record data for study outcomes. However, study team members will only be given access to data necessary for their project roles, described in more detail below. Patients will be assigned a unique identification number and all study data housed outside of REDCap will be de-identified using this number. We believe that in using these methods we will be compliant with the "Standards for Privacy of Individual Identifiable Health Information" under the Health Insurance Portability and Accountability Act of 1996 (HIPAA) Privacy Rule. Participants consented to the intervention will be informed in all cases about their rights as research subjects. They may withdraw at any time during the study without penalty or loss of any healthcare benefit or service to which they are entitled. We will also attempt to reduce shame and performance anxiety as a result of interviews through extensive training of the research assistants.

Potential Benefits

Individuals who participate may gain greater knowledge and understanding about their diabetes and self-care by participating in this research. Additionally, clinics and medical homes can potentially benefit from this intervention research through the dissemination of successful strategies. The potential benefits to the field of health literacy and public health are significant; understanding health literacy in the context of diabetes self-management may lead to future interventions to improve it, which could have a significant impact on public health.

Data Handling and Recordkeeping

The Principal Investigator will carefully monitor study procedures to protect the safety of research subjects, the quality of the data and the integrity of the study. Northwestern University (NU) will be used as a central location for data processing and management. Study data will be collected and managed using NU's REDCap, which is installed on secure NU servers located in HIPAA compliant data centers. UAMS personnel needing access to the data will be provided affiliate Northwestern IDs to access REDCap directly through NU's VPN. REDCap includes a user management system allowing project owners to grant and control varying levels of access to data (e.g. de-identified-only data views) for other users. Study team members will only be given access to data necessary for their project roles. For example, only those involved in scheduling and/or meeting with patients directly will have access to patient identifiers. In addition, Research Assistants (RAs) at each site (six sites total) will be assigned to their own Data Access Group which restricts access to their site's records. Each group is blinded to all other data/records. Those managing and analyzing the data will only have access to de-identified data.

Data Analysis

Baseline characteristics and demographics will be summarized overall and by clinic using descriptive statistics (mean \pm standard deviation for continuous variables, frequencies and percentages for categorical variables, and medians/quartiles as appropriate for ordinal variables). Analyses across all relevant outcomes (i.e., those corresponding to H₁-H₆) will mirror one another in general, with primary outcome being defined as HbA1c levels at six months. Secondary outcome measures include disease and treatment knowledge scores, self-efficacy scores, adherence to self-care behaviors, diabetes-related distress, diabetes-related quality of life and other clinical outcomes (blood pressure, LDL, cholesterol, BMI). Survey data will be collected at baseline, 3 and 6 months; clinical data will be collected at baseline, 3, 6, 9, and 12 months. The primary time point of interest for H₁-H₅ is three-month follow up and for clinical outcomes (H₆) is six-month follow-up, but subjects will be followed through 12 months in order to examine sustainability. We will assume missing data are missing at random, and analyses will consist of parametric statistical tests. Relevant statistical assumptions will be assessed as appropriate, and nonparametric analyses and/or transformations of variables will be explored in the event of violations.

Aim 1 analysis for each outcome will consist of an analysis of covariance (ANCOVA) in which overall mean (μ) follow-up outcome (e.g., HbA1c at 6 months) across groups will be modeled as follows:

$$\mu_i = \beta_0 + \beta_1 I(ACP intervention_i) + \beta_2 (Baseline_i) + \epsilon_i,$$

where *i* corresponds to the individual subject (*i*=1,...,*total N*), β_0 serves as an intercept, β_1 serves as the intervention effect [*I*(*ACP intervention*_i) is an indicator variable for active ACP intervention arm], β_2 represents the effect of baseline value of the corresponding outcome variable, and ϵ_i represents random error. Primary analyses will test the null hypothesis H_0 : $\beta_1 = 0$ against the twosided alternative at the 5% level of significance. Similar analyses will be employed for all relevant outcomes at three and/or six-month follow-up (to examine efficacy/effectiveness) and 12-month follow-up (to examine sustainability). Baseline variables (demographics, comorbidities, health literacy, etc.) will be explored one at a time, in turn, for association with outcome(s), and where appropriate, models will adjusted for significant baseline prognostic variables. Exploratory analyses will employ linear mixed effects models that include a fixed treatment arm, baseline value, relevant prognostic variables, and time effects along with a random subject effect in order

to account for within-subject association among outcome observations. Exploratory analyses will involve inclusion of a fixed change-point or spline term(s) to examine changes in slope over different time periods and/or higher order/interaction terms. In order to examine whether there may a difference across clinic, a random clinic effect will be examined as well, and where appropriate, subgroup analyses by clinic will be employed.

To address Aim 2 (H₇), the subjects will be classified by literacy level (lower literacy or higher literacy), and above analyses will be repeated within each arm but include an indicator for literacy group. Further, the primary model (above) will be modified to include a literacy level effect and corresponding arm-by-literacy level interaction term.

To address Aim 3, we will analyze only those subjects randomized to the ACP intervention arm. We will examine association of (a) number of contacts with each subject and (b) length of contact time, with each relevant outcome variable (H_1 - H_6) at follow-up via a linear model as above. Each model will include an intercept, baseline value for the relevant variable, and variable (a) and/or (b), along with any additional demographics/prognostic variables found relevant in Aims 1 and 2.

Analyses will follow an intent-to-treat (ITT) principle in which all subjects enrolled in the study, regardless of adherence to the study protocol, will be analyzed according to the arm to which they were randomized. Sensitivity analyses will involve the "as treated" dataset. Additional sensitivity analyses will examine multiple imputation methods such as: "best-case", "worst-case", null scenario, and propensity score methods. These multiple imputations will result in no less than five imputed datasets from which we may obtain at least five overall parameter estimates with corresponding standard errors. From these, we will estimate an overall average for all primary and secondary outcomes with appropriate standard errors to determine whether overall conclusions are sensitive to these missing data.⁴² In cases where data may not be assumed MAR (i.e., we suspect non-ignorable missingness), we will explore pattern mixture models and/or selection modeling to conduct further sensitivity analyses.

Power and Sample Size Considerations

Power and sample size calculations were based on primary outcome of HbA1c at six months, assuming an independent two-sample t-test, type I error rate of 5%, and equal variances across arms (1.9, according to previous data). Note that primary outcome analyses will employ ANCOVA, and as a result, the power calculations presented here are considered conservative since we anticipate the inclusion of baseline values in ANCOVA to result in better precision in estimating an intervention effect. We plan to enroll 750 subjects, with minimal anticipated dropout: 90% retention at six months (n= 675, 337 per arm) and 84% retention at 12 months (n=630, 315 per arm). For our primary outcome at 6 months, we will be able to detect a clinically meaningful difference in HbA1c across arms of \geq 0.43 with 80% power. With sample size set by the primary outcome of HbA1c at 6 months, we also present differences we will be able to detect with at least 80% power for the secondary clinical outcome of systolic blood pressure and for the subgroup analyses.

Qualitative provider/clinic barriers and facilitators to implementation

To address aim 4: Determine the fidelity of all intervention components, and explore any identified patient, provider (physician, nurse, health coach), and/or health system barriers to implementation, qualitative descriptions of health systems barriers to implementation will be collected from health coaches, nurses, physicians, and clinic leadership/administration. (see

Appendices C & D, moderator's guide). Interviews and focus groups will be transcribed verbatim and verified for accuracy. Transcripts will be coded using NVIVo software. In addition, [name] notes taken during focus groups will be saved in Microsoft Word. These will also be entered using statistical software. The constant comparative method of grounded theory will be used to identify developing themes. Commonalities and differences in perspective understanding beliefs acceptance knowledge between patients and providers and oncologist and PCP will be analyzed across sub populations.

Ethical Considerations

This study will be conducted in accordance with all applicable government regulations and University of Arkansas for Medical Sciences research policies and procedures. This protocol and any amendments will be submitted and approved by the UAMS Institutional Review Board (IRB) to conduct the study.

Dissemination of Data

Results of this study may be used for presentations, posters, and/or publications. The publications will not contain any identifiable information that could be linked to a participant.

References

- Centers for Disease Control and Prevention. Age-Adjusted Rate per 100 of Civilian, Noninstitutionalized Population with Diagnosed Diabetes, by Race, United States, 1980-2011. *Division of Diabetes Translation, National Center for Chronic Disease Prevention and Health Promotion* 2014;Available at: URL: http://www.cdc.gov/diabetes/statistics/prev/national/figbyrace.htm.
- 3. U.S.Department of Health and Human Services OoDPaP. Healthy People 2020: Diabetes. 2014. Washington, DC.

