- 4. Determine the fidelity of all intervention components, and explore any identified patient, provider (physician, nurse, health coach), and/or health system barriers to implementation.
- 5. Assess the costs associated with implementing the ACP intervention from a health system perspective.

Study Design and Procedures

We will conduct a 2-arm, patient-randomized, pragmatic trial among 750 patients in Arkansas with type 2 diabetes to test the effectiveness and fidelity of a multifaceted, health coachled, low literacy, self-management intervention to improve behavioral and clinical outcomes compared to enhanced usual care in level 3 patient centered medical homes. Enhanced usual care differs from standard diabetes care because enhanced usual care includes patient resources associated with PCMH (team-based care, electronic health records, and care coordination). Eligible, consented patients will be followed for 1 year post baseline interview. Those receiving the ACP intervention will be administered the ACP health literacy strategy at baseline, with 'frontloaded' telephone or in-person follow-up education approximately every 3 months, counseling and action-planning occurring at approximately 2 weeks, 4 weeks, and 8 weeks and then monthly between guarterly clinical visits. In-person, 'point-of-care' counseling sessions will occur guarterly, coinciding with diabetes routine clinical visits. We intentionally aimed to optimize the number of 'touch points' over 1 year, taking into account a reasonable workload for health coaches. Addressing Aim 3, which seeks to ascertain the minimum number of action plans necessary to achieve clinical diabetes goals, or an increasing benefit is seen with more touch points (no threshold). Primary outcomes include intermediary biomarkers indicative of proper disease selfmanagement (HbA1c, blood pressure, LDL cholesterol). In addition, secondary outcomes to be measured include diabetes and treatment-related knowledge, self-efficacy, disease-related distress and quality of life, activation, health behaviors and health services utilization. To determine the reliability and costs associated with delivering the intervention, we will also closely monitor the implementation process and evaluate the fidelity of the components and strategies.

		hanced Usual Care and Intervention
	STANDARD	DIABETES MEDICAL CARE
		In Both Arms
Care Management	of medical care	rting
		AND SELF-MANAGEMENT SUPPORT
	'Enhanced" Usual Care Arm	Intervention Arm

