materials	 ADA 'Living Well with Diabetes' Workbook: 69 page booklet, workbook format Written at 7th grade level 12,250 words 7 chapters: understanding diabetes, blood glucose meal planning, physical activity, medication, overall health, & tools Chapters arranges in sequence of review 	 ACP 'Living with Diabetes' Guide: An everyday guide for you and your family Colorful 56 page booklet Written at a 5th grade level 5,751 words Developed with providers and patients nationally. Addresses topics they identified as most important: understanding DM, eating right, being active, checking blood sugar, taking medicine, keeping feet healthy and learning about insulin Designed to be easily understandable across literacy levels using plain language, conversational tone, limited information and 96 descriptive photographs
counseling	 15 minute, in-person session with clinic nurse to review content in ADA diabetes booklet and answer any patient questions Basic orientation of nurses to the ADA workbook and process for reviewing information with patients completed in 	 Focused on behavior and small actionable steps for behavior change 15 min evidenced-based in-person education and counseling sessions with health coach Introduce and review each chapter of the guide. Use guide as teaching tool Use motivational interviewing skills to engage pt. Elicit info on what they know and do. Counseling based on behavior change model focused on facilitating goal
	 preparation phase This and other diabetes education varies by provider, practice, and time 	 setting. The patient (not provider) creates specific behavioral action plan. Coach elicits domain patient is willing to work on and coaches the patient to create a small, easily achievable behavior they are willing to initiate this week. The coach then asks: On a scale from 1 to 10: How sure are you that you can carry out this action plan during the next week? How important is carrying out this action plan to you? Identify new action plan if either patient rating is 7 or below

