Follow-Up	 Follow-up at scheduled clinic visits approximately every 3 months No standard, practices vary over time 	 In-person 15 min education & counseling sessions at approximately 3,6, 9, and 12 months with health coach Phone calls with health coach to inquire about progress on action plans, use motivational interviewing to problem-solve or establish new action plans Bi-weekly post-visit phone calls for first 3 months (2,4, and 8 weeks after baseline encounter) Monthly post-visit phone calls between clinic visits after 3 months (4,5,7, 8, 10, and 11 month calls) Survey data will be collected at baseline, 3 and 6 months; clinical data will be collected following baseline, 3, 6, 9, and 12 months
Clinical Integration	 Documentation in EHR with nursing note whether post visit DM counseling occurred (yes or no) and when 	 EHR tools and prompts for health coach follow-up phone calls or face-to-face meetings, documentation of call attempts Health coach received information on patients' glycemic control (HbA1c lab value at visit) prior to patient counseling session Health coach documents in EHR every month using care note function: describes and provides update for PCP detailing patient's diabetes action plans and progress towards goals Email to PCP via EHR if patient does not complete 2 consecutive action plans, identifying barriers is known, or if any concerns arise

Figure 1. Study flow chart

Study Sites

The project will engage six UAMS Regional family medicine clinics in regions of Arkansas that are underserved and rural. All clinics have implemented the Patient-Centered Medical Home (PCMH) model of care and achieved the highest level of accreditation, level 3. All regional medical centers have participated in implementation of health literacy best practices using the Agency for Healthcare Quality and Research (AHRQ)'s Health Literacy Universal Precautions Toolkit for the last two years. The majority of patients served by these clinics is low-income and there is a high rate of chronic disease in each clinic's patient population. There are approximately 2,205 total patients at these clinics with HbA1c greater than 7.5%, which denotes that an individual has perhaps not yet achieved tight glycemic control and therefore may be at elevated risk for diabetes-related complications. All clinics have agreed to participate. Letters of support from the clinic directors are included.

Preliminary Studies

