eligibility criteria: 1) 21 years of age or older, and 2) English speaking. The exclusion criteria are: 1) uncorrectable vision, hearing, or cognitive impairments that limit the ability to access intervention materials; and 2) those who are too ill to participate due to recent hospitalization or other recently documented illnesses. The English speaking criterion is included because not all measures and materials involved in the clinical trial are available in languages other than English.

We will recruit 750 patients (n=375 per arm). Eligible participants will be identified through EHR queries. The Central RA/care coordinator will make all pre-visit calls to eligible patients. The Central RA/care coordinator will provide information about the study in the pre-visit call, and ask if the patient is interested in participating in the study. If the patient is interested, the Central RA/care coordinator will ask the patient to meet with the Site RA for about 1 hour, review and sign the informed consent document, and begin baseline data collection. At each clinic, the Site RA will receive lists of interested patients and their scheduled appointment times, greet patients upon check in and escort them to a private space, explain the study, answer any questions the patient might have, and obtain written consent. The Site RA will then collect baseline data through a structured interview. Participants who are randomized to the intervention arm will also meet with the health coach for about 30 minutes. Participants will also meet with their provider if scheduled.

Informed Consent

Participants will provide written consent using procedures approved by the Institutional Review Board (IRB) of UAMS. Recruitment will be done over the phone by the Central RA/care coordinator. Patients who are interested in participating will be asked to meet in person with a Site RA for about 1 hour. When the patient arrives for their appointment, the Site RA will review the consent form, answer any questions, obtain written consent, then administer the brief baseline in-person interview. Informed consent documents will be composed at a fifth grade or lower reading level, be summarized, followed by a brief "teach back" to confirm understanding of key points of consent. The formal consent of each subject, using the IRB-approved consent form, will be obtained before that subject is submitted to any study procedure.

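### The intervention description is inconsistent on the mode of quarterly coach contacts and on coach session length, so Aim 4 lacks one written reference for delivery as planned

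*Combined protocol and SAP*

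**What the plan says.** **Quarterly mode.** The narrative in Study Design and Procedures offers "telephone or in-person follow-up education approximately every 3 months". The next sentence reads "In-person, 'point-of-care' counseling sessions will occur guarterly, coinciding with diabetes routine clinical visits". The Follow-Up row of the table comparing the arms also makes the sessions at about 3, 6, 9 and 12 months in person, at 15 minutes each.

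**Session length.** The counseling row of the same table, which is separate from the Follow-Up row, specifies "15 min evidenced-based in-person education and counseling sessions with health coach". The Recruitment section, describing the visit at which consent and baseline data are obtained, says "Participants who are randomized to the intervention arm will also meet with the health coach for about 30 minutes".

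**Calls.** The Follow-Up row gives "Bi-weekly post-visit phone calls for first 3 months (2,4, and 8 weeks after baseline encounter" and then "Monthly post-visit phone calls between clinic visits after 3 months (4,5,7, 8, 10, and 11 month calls". The narrative gives "counseling and action-planning occurring at approximately 2 weeks, 4 weeks, and 8 weeks and then monthly between guarterly clinical visits".

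**Use of the schedule.** Under Fidelity outcomes, coach logs show for each follow-up interval whether the patient was reached and, if so, the time spent. No planned number of contacts, required length, permitted mode or adherence threshold is stated. The coach training text under Preparation phase describes a tracking system for the number of contacts (by phone and in person), their length, the attempts made and the content.

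**The concern.** Aim 4 asks how faithfully the intervention was delivered, and that needs a statement of what was planned. As written, a quarterly session held by telephone agrees with one sentence of the design section and departs from the next. A 15-minute coach session at baseline matches the table, but is half the time given under Recruitment if both describe the same encounter. Two people auditing the same log could therefore reach different answers and each cite the protocol. Aim 5 has the same difficulty wherever planned coach time is used.

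A related matter concerns Aim 3, which relates the number and length of contacts to outcome within the intervention arm. Preparation phase has a health coach trained at each clinic, and the Randomization section describes considerable diversity among the clinics. The Aim 3 model names an intercept, the baseline value, the contact variables and prognostic variables found relevant earlier, but not site. If contact number or time varies by clinic or coach for any reason, that variation could be read as a patient-level dose effect.

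**Working it through.** No sample-size formula applies. The check is to set the statements side by side and count.

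**1. Number of contacts: do the narrative and the table agree?**
- Early calls: weeks 2, 4 and 8 in both places, so 3.
- Later calls: months 4, 5, 7, 8, 10 and 11 in the table, so 6. This fits the narrative's monthly contacts between quarterly visits.
- Quarterly sessions: months 3, 6, 9 and 12, so 4.
- Follow-up contacts: 3 + 6 + 4 = 13, or 14 with the baseline session. By the six-month primary time point: 3 + 2 + 2 = 7 follow-up contacts.

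The listed time points give one count. The gaps to weeks 2, 4 and 8 are 2, 2 and 4 weeks, so the label bi-weekly does not fit the last gap. That is a fault in the label, not in the list.

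**2. Quarterly mode**

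| Place | Mode of the contact about every 3 months |
|---|---|
| Study Design and Procedures, first statement | telephone or in person |
| Study Design and Procedures, next sentence | in person |
| Table, Follow-Up row | in person, 15 minutes |

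The first statement concerns education and the second concerns counseling, so one might try to treat them as separate contacts. The Follow-Up row does not allow this, because it combines education and counseling in one in-person session. The statements remain unreconciled.

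**3. Session length**

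Inputs: 15 minutes (counseling row), about 30 minutes (Recruitment), and four quarterly sessions of 15 minutes (Follow-Up row). Scheduled in-person minutes per patient = baseline session + 4 × 15.
- 15-minute baseline session: 15 + 60 = 75 minutes.
- 30-minute baseline session: 30 + 60 = 90 minutes.
- Difference: 15 minutes, and 15/75 = 20%.
- Over the planned 375 intervention patients: 375 × 15 = 5,625 minutes, or 5,625/60 = 93.75 coach-hours.

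These differences apply only if the two lengths describe the same session. If quarterly sessions may be by telephone, the only in-person time assured is the baseline session, at 15 or about 30 minutes.

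**4. Which analyses use these inputs?**
- Primary HbA1c analysis: ANCOVA by randomized arm. Neither it nor the sample size uses planned contacts or minutes.
- Aim 3: observed number of contacts and observed contact time. It can be run without a planned dose.
- Aim 4: the log records reached or not, and time spent, per interval. Judging delivery against plan needs the schedule.
- Aim 5: delivered time can be taken from the log. Only planned time depends on the conflicting text.

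**5. Cost of a site term in Aim 3**

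Six clinics need 6 − 1 = 5 parameters. With 90% retention, the plan expects 337 patients per arm at six months, so the loss of precision from the parameter count alone is small.

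**The case against.** The best defence is that these are drafting slips in a self-described pragmatic trial with approximate timings. Three parts of it carry weight.

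First, the counseling row never says baseline, and a first meeting of about 30 minutes could include an introduction and handing over the guide as well as a 15-minute counseling session. That is possible, but the documents do not say it, so the length point is an unresolved tension and not a proven contradiction.

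Second, the narrative sentence on quarterly mode is a run-on list in which telephone or in-person may have been meant to cover all the follow-up contacts that it goes on to name. That is also possible. However, Preliminary Studies calls the approach telephone based, and the gift-card text under Randomization allows a phone call for the 3-month follow-up (perhaps only the survey contact). A telephone reading is therefore not far-fetched.

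Third, contact number, length and phone or in-person contact are already tracked, so Aim 3 and the delivered-time part of Aim 5 do not depend on resolving the text. This stands in full.

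On site in Aim 3, the Aim 1 text does mention examining a random clinic effect, and the Aim 3 model may carry forward prognostic variables. Neither commits the Aim 3 model to a site term.

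A reader might also infer that clinics were given different instructions and delivered different doses. The documents do not show this: coach training is held in a central location, and EHR prompts support the coach's calls and meetings.

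**Conclusion.** The concern holds in a limited form. Quarterly mode and session length are each stated in two ways that no text reconciles, and the bi-weekly label is a wording slip. The size is 75 or 90 scheduled in-person minutes per patient, assuming that the two lengths describe the same session, and about 94 planned coach-hours over 375 patients on the same assumption. What suffers is the reference for delivery as planned in Aim 4 and planned coach time in Aim 5. The primary HbA1c comparison and its power are untouched.

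A reader might take the label literally and infer six early calls (weeks 2, 4, 6, 8, 10 and 12), hence 1 + 6 + 6 + 4 = 17 contacts, and conclude that three calls delivered is 3/6 = 50% fidelity. The documents do not support this. Weeks 2, 4 and 8 are listed in both the narrative and the table, no place lists six early calls, and no percentage fidelity score is defined.

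The Aim 3 recommendation does not rest on sites having read the protocol differently. It rests on each clinic having its own coach, on the clinics being described as diverse, and on site not being named in the model.

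**What to change.** 1. Reconcile the Study Design and Procedures narrative, the counseling and Follow-Up rows of the table, and the Recruitment text into one contact schedule. For each contact, give its time, mode and planned minutes, and say what the baseline coach meeting covers. Which version is right is for the sponsor to decide; this review does not choose.
2. Make the frequency label agree with the time points in that schedule.
3. Name that schedule as the reference for Aim 4 and as the source of planned coach time for Aim 5.
4. Include site in the Aim 3 models. This removes differences between clinics, and between coaches to the extent that each clinic keeps one coach. It does not remove differences in engagement among patients within a clinic.

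The cost is a protocol clarification, one table and five degrees of freedom in Aim 3. No added patients, staff or data items are needed, since the tracking system already covers the number, length and phone or in-person nature of contacts.
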